5.5 Diet/Activity/Other Considerations

5.5.1 Diet

Subjects should maintain a normal diet unless modifications are required to manage an AE such as diarrhea, nausea or vomiting.

5.5.2 Contraception

Pembrolizumab may have adverse effects on a fetus in utero. Furthermore, it is not known if pembrolizumab has transient adverse effects on the composition of sperm. Non-pregnant, non-breast-feeding women may be enrolled if they are willing to use 2 methods of birth control or are considered highly unlikely to conceive. Highly unlikely to conceive is defined as 1) surgically sterilized, or 2) postmenopausal (a woman who is ≥ 45 years of age and has not had menses for greater than 1 year will be considered postmenopausal), or 3) not heterosexually active for the duration of the study. The two birth control methods can be either two barrier methods or a barrier method plus a hormonal method to prevent pregnancy. Subjects should start using birth control from study Visit 1 throughout the study period up to 120 days after the last dose of study therapy.

The following are considered adequate barrier methods of contraception: diaphragm, condom (by the partner), copper intrauterine device, sponge, or spermicide. Appropriate hormonal contraceptives will include any registered and marketed contraceptive agent that contains an estrogen and/or a progestational agent (including oral, subcutaneous, intrauterine, or intramuscular agents).

Subjects should be informed that taking the study medication may involve unknown risks to the fetus (unborn baby) if pregnancy were to occur during the study. In order to participate in the study, they must adhere to the contraception requirement (described above) for the duration of the study and during the follow-up period defined in section 7.2.2-Reporting of Pregnancy and Lactation to the Sponsor-Investigator and to Merck. If there is any question that a subject will not reliably comply with the requirements for contraception, that subject should not be entered into the study.

5.5.3 Use in Pregnancy

If a subject inadvertently becomes pregnant while on treatment with pembrolizumab, the subject will immediately be removed from the study. The site will contact the subject at least monthly and document the subject's status until the pregnancy has been completed or terminated. The outcome of the pregnancy will be reported to Merck without delay and within 24 hours to the Sponsor-Investigator and within 2 business days of investigator knowledge if the outcome is a serious adverse experience (e.g., death, abortion, congenital anomaly, or other disabling or life-threatening complication to the mother or newborn).

The study investigator will make every effort to obtain permission to follow the outcome of the pregnancy and report the condition of the fetus or newborn to Merck. If a male subject impregnates his female partner the study personnel at the site must be informed immediately and the pregnancy reported to Merck and followed as described above and in Section 7.2.2.

5.5.4 Use in Nursing Women

It is unknown whether pembrolizumab is excreted in human milk. Since many drugs are excreted in human milk, and because of the potential for serious adverse reactions in the nursing infant, subjects who are breast-feeding are not eligible for enrollment.

5.6 Subject Withdrawal/Discontinuation Criteria

Subjects may withdraw consent at any time for any reason or be dropped from the trial at the discretion of the investigator should any untoward effect occur. In addition, a subject may be withdrawn by the investigator if enrollment into the trial is inappropriate, the trial plan is violated, or for administrative and/or other safety reasons. Subjects who require cessation of study therapy but do not withdraw consent may remain in standard follow-up for up to 5 years.

A subject must be discontinued from the trial for any of the following reasons:

- The subject or legal representative (such as a parent or legal guardian) withdraws consent.
- Confirmed radiographic disease progression
- Unacceptable adverse experiences as described in Section 5
- Intercurrent illness that prevents further administration of treatment
- Investigator's decision to withdraw the subject
- The subject has a confirmed positive serum pregnancy test
- Noncompliance with trial treatment or procedure requirements
- The subject is lost to follow-up
- Administrative reasons

The End of Treatment and Follow-up visit procedures are listed in Section 6 (Protocol Flow Chart) and Section 7.1.5 (Visit Requirements). After the end of treatment, each subject will be followed for 30 days for adverse event monitoring (serious adverse events may be collected for 90 days after the end of treatment as described in Section 7.2.3.1). Patients may have post-treatment follow-up for disease status up to 5 years at longest, or until disease progression, initiating a non-study cancer treatment, withdrawing consent, or becoming lost to follow-up.

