6.0 TRIAL FLOW CHART

6.1 Study Flow Chart

	Screening Period	Treatment Phase			End of treatment ⁶	Long-term Follow-up ⁷
		Window Cycles (1-6)	Response assessment ⁸	Continuation Cycles (7-18) ⁹		
Scheduling and Timing	-42 to -1d	+/- 3d		+/- 3d		
Informed consent	X					
Inclusion/Exclusion criteria	X					
Medical history	X					
Medication review (prior and concomitant)	X	X		X		
Trial treatment administration		X		X		
Post-study anticancer therapy status						X
Survival status						X
Vital signs	X	X		X	X	
Physical exam	X	X		X	X	
ECOG performance status	X	X		X	X	
Adverse event assessment ¹	X	X		X	X	
CBC and differential	X	X	X	X	X	
Comprehensive metabolic panel and LDH	X	X	X	X	X	
HepB SAg, Hep B Core Ab, HepC Antibody and HIV screen	X					
Urinalysis	X					
T3, FT4, and TSH	X	X		X	X	
PT/INR and aPTT	X					
Correlative studies blood draw	X		X		X	
Bone marrow studies ²	X					X
Pregnancy test ³	X					
Tumor assessment ⁵	X	X	X	X	X	
Archival Tissue collection ⁴	X					

¹Adverse events will be recorded from the time of a subject signing consent up until 30 days after the last dose of pembrolizumab, or 90 days after the last dose of pembrolizumab in the case of serious adverse events.

²If bone marrow involvement by iBCL was previously shown then repeat bone marrow exam at screening is not required as it is assumed positive. Otherwise, bone marrow studies include aspirate and unilateral biopsy and should be performed at screening unless a waiver is approved by the study Sponsor-Investigator or sub-Investigator. If all bone marrow studies are negative at screening, these do not need to be repeated. If bone marrow status is unknown or positive at screening, patients will need to have bone marrow study for confirmation of a CR.

³Pregnancy test is only required in women of childbearing potential.

⁴Archived tumor samples are requested for pathologic confirmation and biomarker analysis. If an archived specimen is not available or contains insufficient material, a fresh tumor biopsy (if clinically feasible) will be requested. Correlative studies may be performed on any available tissue.

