⁵Tumor assessment labs and/or imaging (see section 7.1.2.5) will be performed prior to cycle 4 (within 7 days of scheduled treatment dose) during the window phase. Tumor assessment will be performed prior to cycle 7 (within 7 days of scheduled treatment dose) to determine eligibility for continuation on study in continuation phase. Tumor assessment labs and/or imaging will be performed prior to cycles 11 and 15 (within 7 days of scheduled treatment dose) during the continuation phase, as applicable. Tumor assessment labs and/or imaging will be performed at end-of-treatment evaluation only for subjects who did not have tumor assessment labs and/or imaging performed within 60 days of end-of-treatment. Tumor assessment labs and/or imaging will also be performed as indicated per clinical standard of care (e.g. as appropriate for disease, to evaluate clinical suspicion of disease progression). Patients who have stable disease or asymptomatic radiologic disease progression prior to cycle 7 will remain in the window phase with restaging prior to cycle 10 to evaluate for pseudoprogression or delayed response. Patients who have restaging prior to cycle 10 are not required to have tumor assessments prior to cycle 11. Patients who have radiologic disease progression with doubling of tumor size prior to cycle 7 will be categorized as hyperprogression and will not proceed to the continuation phase.

⁶End-of-treatment evaluations should be done within 30 days (+/- 14 days) of the last dose of pembrolizumab or prior to the start of a new anti-cancer drug, whichever is first.

⁷Long-term follow-up should be done according to the patient's physician standard of care. This may be performed at patients' local physician's offices. Long-term follow-up will assess survival and disease progression; for clarification, subjects may be contacted by the study team until death, subject withdrawal of consent, lost to follow-up, or study termination, whichever occurs first.

⁸Response assessment will be performed prior to cycle 7 (within 7 days of scheduled treatment dose) only for those subjects that complete 6 cycles of treatment in the window phase.

⁹During treatment in the continuation phase, clinical assessment (physical exam including performance status, adverse event and medication review) will be performed on day 1 (+/- 3 days) of each odd-numbered cycle only, or as clinically indicated. Studies performed for response assessment⁹ do not need to be repeated prior to cycle 7.

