7.1.5.3 End-of-treatment Visit

Thirty days (+/- 14 d) after the last dose of pembrolizumab, irrespective of cause of cessation, an end-of-treatment visit should be performed. However, if a subject requires additional anti-cancer therapy, the off-study visit may occur earlier.

The off-study visit will include laboratory studies, medical history, physical exam, remission status, concomitant medications, adverse events, and documentation of any ECI and subsequent management, as in Section 6.0. All AEs that occur prior to the end-of-treatment visit should be recorded. Subjects with an AE of Grade > 1 will be followed until the resolution of the AE to Grade 0-1 or until the beginning of a new anti-neoplastic therapy, whichever occurs first. SAEs that occur within 90 days of the end of treatment or before initiation of a new anti-cancer treatment should also be followed and recorded.

After the end-of-study visit, additional follow-up will be conducted as per routine standard of care for up to 5 years unless other criteria for withdrawal are met (see Section 5.6). Long-term follow-up may be performed at patients' local physician's offices. Long-term follow-up will assess survival and disease progression; for clarification, subjects may be contacted by the study team until death, subject withdrawal of consent, lost to follow-up, or study termination, whichever occurs first.

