8.3.2.3 Time to next therapy

Time to additional anti-neoplastic treatment will be measured from the time of first study drug administration until the date of the first subsequent therapy given to treat the iBCL. Data for subjects that have not received additional anti-neoplastic therapy will be censored at the date of last known contact.

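### Section 5.6 conflicts with the flow chart and other sections on whether trial contact ends at progression; if a site follows 5.6, time to next therapy is informatively censored.

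*Combined protocol and SAP*

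**What the plan says.** Passages that point to an end at progression:

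- Section 5.6 opens its mandatory list with "A subject must be discontinued from the trial for any of the following reasons". One entry is "Confirmed radiographic disease progression". The stem speaks of the trial, not only of study treatment.
- The last paragraph of 5.6 says: "Patients may have post-treatment follow-up for disease status up to 5 years at longest, or until disease progression, initiating a non-study cancer treatment". Consent withdrawal and loss to follow-up complete that list.
- Section 7.1.5.3 provides up to 5 years of follow-up "unless other criteria for withdrawal are met (see Section 5.6").

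Passages that point to contact after progression:

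- Section 5.6, first paragraph: "Subjects who require cessation of study therapy but do not withdraw consent may remain in standard follow-up for up to 5 years".
- Section 6.1 marks the row "Post-study anticancer therapy status" in the long-term follow-up column, and likewise survival status.
- Footnote 7 to the flow chart: "subjects may be contacted by the study team until death, subject withdrawal of consent, lost to follow-up, or study termination". Section 7.1.5.3 repeats this after its cross-reference to 5.6. Neither progression nor new therapy is among the end points of contact.
- Section 7.1.1.5.2 calls for review of every new anti-neoplastic treatment begun after the last dose, with no stop at progression.

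TNT is a secondary efficacy outcome (section 3.2). Section 8.3.2.3 runs it from first study drug to first subsequent therapy for the lymphoma, with this censoring rule: "Data for subjects that have not received additional anti-neoplastic therapy will be censored at the date of last known contact".

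**The concern.** Next therapy for lymphoma commonly follows progression. The TNT censoring date is the last known contact, so the estimate depends on when contact stops, and the protocol gives two answers. Under the mandatory wording of 5.6, a patient who progresses at month 6 could be closed at about that time. A therapy begun at month 10 would not be recorded, and TNT would be censored near month 6.

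Kaplan-Meier estimation treats such a patient as having the same future risk of next therapy as those still followed. Here the reason for censoring is the event that raises that risk, so the censoring is informative and TNT is biased upwards. Therapies that were never recorded cannot be restored at analysis. If different staff or local physicians act on different passages, the result also depends on whose reading was applied.

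**Working it through.** **1. The passages side by side.**

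| Question | Ends at progression | Continues |
|---|---|---|
| Trial participation | 5.6, mandatory list | 5.6, first paragraph; 2.1 (outcomes for up to 5 years) |
| Disease-status follow-up | 5.6, last paragraph | – |
| Subsequent therapy | 5.6, mandatory list, if read literally | 6.1 row; 7.1.1.5.2 |
| Contact | 7.1.5.3, through its reference to 5.6 | footnote 7; 7.1.5.3, later sentence |

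Ending disease-status follow-up at progression would not by itself harm TNT. The damage comes from the trial-discontinuation stem and from the cross-reference that carries it into 7.1.5.3. The stem is mandatory, while the sentences on contact after progression are permissive (may remain, may be contacted).

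**2. Plan figures.** The documents state none for TNT. Their design power concerns ORR only. The exact two-stage binomial calculation (continue with 5 or more responses in 16, succeed with 13 or more in 33) gives power 0.902 at 50%, against the stated 90%, and type I error 0.045 at 25%. Neither depends on follow-up after progression.

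**3. Size, under assumptions.** Time to progression T is exponential with median 12 months (rate a = ln 2/12 = 0.0578). The gap G to next therapy is exponential with median g = 2, 6 or 12 months (rate b = ln 2/g). A share of 20% start new therapy without recorded progression; those events are seen under either reading, because starting therapy is itself an end point in 5.6. Follow-up is 60 months.

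*True share free of next therapy at 24 months:* 0.2·2^(−24/12) + 0.8·P(T+G > 24), where P(T+G > t) = (b·e^(−at) − a·e^(−bt))/(b − a), or e^(−at)(1 + at) when a = b.

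- g = 2: 0.05 + 0.8 × 0.300 = 0.29
- g = 6: 0.05 + 0.8 × 0.4375 = 0.40
- g = 12: 0.05 + 0.8 × 0.597 = 0.53

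*Contact ends at progression:* only the 20% contribute events, with hazard 0.2a, so Kaplan-Meier tends to 2^(−0.2 × 24/12) = 2^(−0.4) = 0.76 whatever the gap.

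*Events per 33 patients by 60 months:* 33 × 0.2 × (1 − 2^(−5)) = 6.4 if contact ends at progression. With full contact the number is 33 × [1 − 0.2·2^(−5) − 0.8·P(T+G > 60)] = 31.8, 31.2 and 29.1 for g = 2, 6 and 12.

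**4. Other inputs, same formulas.**

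| Median T | Treated without recorded progression | True, g = 2 to 12 | Contact ends at progression |
|---|---|---|---|
| 12 | 0% | 0.30 to 0.60 | 1.00 |
| 12 | 20% | 0.29 to 0.53 | 0.76 |
| 12 | 40% | 0.28 to 0.46 | 0.57 |
| 24 | 20% | 0.54 to 0.70 | 0.87 |

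**5. Relaxing the bound.** Step 3 puts last contact on the progression date. Suppose instead that every patient is observed for w = 3 months (about 90 days) after progression. The observed hazard is then a(0.2 + 0.8bK)/(1 + 0.8aK), with K = (1 − e^(−(b−a)w))/(b − a), or K = w when a = b, and with w replaced by t during the first 3 months. Integrating to 24 months gives 0.40, 0.58 and 0.67 for g = 2, 6 and 12, against the true 0.29, 0.40 and 0.53. The overstatement falls from 0.47, 0.36 and 0.23 to about 0.11, 0.18 and 0.14, but does not vanish.

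**The case against.** The strongest reply is that the plan, read as a whole, already collects what TNT needs.

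- A reader might infer that TNT is censored at progression. Section 8.3.2.3 does not say so; it uses last known contact. The bias is conditional on a site acting on 5.6.
- A reader might infer that 5.6 ends all follow-up. The sentence quoted from its last paragraph covers disease status only. The mandatory list also contains reasons that concern treatment, such as intercurrent illness preventing further dosing, and the section goes on to describe follow-up afterwards, including 5-year standard follow-up once therapy stops. So 5.6 is ambiguous within itself.
- A reader might see 7.1.5.3 as simply contradicting 5.6. It defers to 5.6 and then, by way of clarification, allows contact until death. That can be read as resolving the matter, but the permissive sentence does not switch off the condition stated just before it.
- Last contact would seldom be the progression date. There is an end-of-treatment visit about 30 days after the last dose, and specified adverse events are recorded to 90 days after it. Under the assumed gaps, 1 − 2^(−3/g) = 65%, 29% and 16% of next therapies would fall within 3 months of progression. This stands, and it is why 0.76 is only an upper bound for its scenario. The windows run from the last dose, however. Treatment lasts at most 18 × 3 = 54 weeks, about 12.4 months, so with a 12-month median only about 1 − 2^(−12.4/12) = 51% would progress within that time. Step 5 gives the 3 months to everyone and is generous.
- Section 4.1 describes the early course of indolent disease in general, whereas eligibility requires an indication for treatment. It is weak support for long gaps, so the gap is varied here rather than taken from the text.

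These replies limit the size and the certainty of the effect. They do not remove the conflict.

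**Conclusion.** The follow-up wording is inconsistent and should be reconciled. The documents support a conditional conclusion: if a site follows the trial-discontinuation wording of 5.6, TNT is informatively censored at or soon after progression and is biased upwards.

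For a median time to progression of 12 months, median gaps of 2 to 12 months and 20% treated without recorded progression, the upper bound is an estimate of about 0.76 for 24-month freedom from next therapy against a true 0.29 to 0.53. With 3 months of contact after progression for everyone, the estimate is 0.40 to 0.67. All these inputs are assumed. The direction is the same in every scenario tried; the size is not known.

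TNT is a secondary endpoint with no test or target. ORR, N = 33 and the ORR stopping rules are unaffected.

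**What to change.** Reconcile 5.6 with the flow chart, footnote 7, 7.1.1.5.2 and 7.1.5.3 by defining three separate end points: end of study treatment, end of disease-status assessment, and end of trial contact. Then state that:

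- progression does not end trial contact;
- the start date of the first subsequent therapy for the lymphoma is collected after progression;
- survival status continues to be collected beyond that therapy, until death, consent withdrawal, loss to follow-up, study termination or the 5-year limit.

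Narrow the reference to 5.6 in 7.1.5.3 to match. The treatment-stopping rules should be left for the sponsor to reconcile: sections 2.1 and 4.2.3.1 and flow-chart footnote 5 allow some treatment after initial radiologic progression, and this point takes no position on them.

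The change is one of wording. The flow chart already lists the data items, so no new visits are needed. The cost is some extra calls or record requests for patients who have progressed.

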5.7 Subject Replacement Strategy

Subjects who fail to complete study therapy will not be replaced.

5.8 Clinical Criteria for Early Trial Termination

Early trial termination will be the result of the criteria specified below:

1. Quality or quantity of data recording is inaccurate or incomplete
2. Poor adherence to protocol and regulatory requirements

3. Incidence or severity of adverse drug reaction in this or other studies indicates a potential health hazard to subjects
4. Plans to modify or discontinue the development of the study drug

In the event of Merck decision to no longer supply study drug, ample notification will be provided so that appropriate adjustments to subject treatment can be made.

6.0 TRIAL FLOW CHART

6.1 Study Flow Chart

	Screening Period	Treatment Phase			End of treatment ⁶	Long-term Follow-up ⁷
		Window Cycles (1-6)	Response assessment ⁸	Continuation Cycles (7-18) ⁹		
Scheduling and Timing	-42 to -1d	+/- 3d		+/- 3d		
Informed consent	X					
Inclusion/Exclusion criteria	X					
Medical history	X					
Medication review (prior and concomitant)	X	X		X		
Trial treatment administration		X		X		
Post-study anticancer therapy status						X
Survival status						X
Vital signs	X	X		X	X	
Physical exam	X	X		X	X	
ECOG performance status	X	X		X	X	
Adverse event assessment ¹	X	X		X	X	
CBC and differential	X	X	X	X	X	
Comprehensive metabolic panel and LDH	X	X	X	X	X	
HepB SAg, Hep B Core Ab, HepC Antibody and HIV screen	X					
Urinalysis	X					
T3, FT4, and TSH	X	X		X	X	
PT/INR and aPTT	X					
Correlative studies blood draw	X		X		X	
Bone marrow studies ²	X					X
Pregnancy test ³	X					
Tumor assessment ⁵	X	X	X	X	X	
Archival Tissue collection ⁴	X					

¹Adverse events will be recorded from the time of a subject signing consent up until 30 days after the last dose of pembrolizumab, or 90 days after the last dose of pembrolizumab in the case of serious adverse events.

²If bone marrow involvement by iBCL was previously shown then repeat bone marrow exam at screening is not required as it is assumed positive. Otherwise, bone marrow studies include aspirate and unilateral biopsy and should be performed at screening unless a waiver is approved by the study Sponsor-Investigator or sub-Investigator. If all bone marrow studies are negative at screening, these do not need to be repeated. If bone marrow status is unknown or positive at screening, patients will need to have bone marrow study for confirmation of a CR.

³Pregnancy test is only required in women of childbearing potential.

⁴Archived tumor samples are requested for pathologic confirmation and biomarker analysis. If an archived specimen is not available or contains insufficient material, a fresh tumor biopsy (if clinically feasible) will be requested. Correlative studies may be performed on any available tissue.

⁵Tumor assessment labs and/or imaging (see section 7.1.2.5) will be performed prior to cycle 4 (within 7 days of scheduled treatment dose) during the window phase. Tumor assessment will be performed prior to cycle 7 (within 7 days of scheduled treatment dose) to determine eligibility for continuation on study in continuation phase. Tumor assessment labs and/or imaging will be performed prior to cycles 11 and 15 (within 7 days of scheduled treatment dose) during the continuation phase, as applicable. Tumor assessment labs and/or imaging will be performed at end-of-treatment evaluation only for subjects who did not have tumor assessment labs and/or imaging performed within 60 days of end-of-treatment. Tumor assessment labs and/or imaging will also be performed as indicated per clinical standard of care (e.g. as appropriate for disease, to evaluate clinical suspicion of disease progression). Patients who have stable disease or asymptomatic radiologic disease progression prior to cycle 7 will remain in the window phase with restaging prior to cycle 10 to evaluate for pseudoprogression or delayed response. Patients who have restaging prior to cycle 10 are not required to have tumor assessments prior to cycle 11. Patients who have radiologic disease progression with doubling of tumor size prior to cycle 7 will be categorized as hyperprogression and will not proceed to the continuation phase.

⁶End-of-treatment evaluations should be done within 30 days (+/- 14 days) of the last dose of pembrolizumab or prior to the start of a new anti-cancer drug, whichever is first.

⁷Long-term follow-up should be done according to the patient's physician standard of care. This may be performed at patients' local physician's offices. Long-term follow-up will assess survival and disease progression; for clarification, subjects may be contacted by the study team until death, subject withdrawal of consent, lost to follow-up, or study termination, whichever occurs first.

⁸Response assessment will be performed prior to cycle 7 (within 7 days of scheduled treatment dose) only for those subjects that complete 6 cycles of treatment in the window phase.

⁹During treatment in the continuation phase, clinical assessment (physical exam including performance status, adverse event and medication review) will be performed on day 1 (+/- 3 days) of each odd-numbered cycle only, or as clinically indicated. Studies performed for response assessment⁹ do not need to be repeated prior to cycle 7.

